8.6.2 Statistical Methods for Safety Analyses

Analysis of the safety data from the infant stage of the study will be based on the combined data from Stage 2 Part I and Stage 2 Part II.

There are no safety hypotheses for this study. Safety and tolerability will be assessed by clinical review of all relevant parameters including AEs, within both the adult and infant cohorts. For the adult cohort, within group summaries of safety (incidence rates and 95% CIs) will be provided for each V114 arm following a single dose. For the infant cohort, comparisons will be made between the V114 arms and Prevnar 13TM following each dose, and across all doses as outlined below.

The analysis of safety results for the infant cohort will follow a tiered approach ([Table 5](#)). The tiers differ with respect to the analyses that will be performed. The Tier 1 safety endpoints in this study consist of the solicited injection-site (redness, swelling, and pain/tenderness) and solicited systemic (irritability, drowsiness, hives/welts, and appetite lost) AEs from the infant cohort and will be subject to inferential testing for statistical significance with p-values and 95% confidence intervals provided for between-group comparisons (V114 versus Prevnar 13TM). Other safety parameters will be considered Tier 2 or Tier 3. Tier 2 parameters will be assessed via point estimates with 95% confidence intervals provided for between-group (V114 versus Prevnar 13TM) comparisons; only point estimates by treatment group are provided for Tier 3 safety parameters.

Adverse experiences that are not pre-specified as Tier-1 endpoints will be classified as belonging to "Tier 2" or "Tier 3", based on the number of events observed. Membership in Tier 2 requires that at least 4 subjects in any treatment group exhibit the event; all other adverse experiences will belong to Tier 3.

The threshold of at least 4 events was chosen because the 95% confidence interval for the between-group difference in percent incidence will always include zero when treatment groups of equal size each have less than 4 events and thus would add little to the interpretation of potentially meaningful differences. Because many 95% confidence intervals may be provided without adjustment for multiplicity, the confidence intervals should be regarded as a helpful descriptive measure to be used in review, not a formal method for assessing the statistical significance of the between-group differences in adverse experiences.

For this protocol, the broad clinical and laboratory AE categories consisting of the percentage of subjects with any AE, a vaccine related AE, a serious AE, an AE which is both vaccine-related and serious, and who discontinued due to an AE will be considered Tier 2 endpoints. For Tier 2, 95% confidence intervals will be provided for between-treatment differences in the percentage of subjects with events; these analyses will be performed using the Miettinen and Nurminen method (1985) [8], an unconditional, asymptotic method.

Table 5 Analysis Strategy for Infant Cohort Safety Parameters

Safety Tier	Safety Endpoint [†]	p-Value	95% CI for Treatment Comparison	Descriptive Statistics
Tier 1	Solicited Injection-Site and Solicited Systemic AEs	X	X	X
Tier 2	Any AE		X	X
	Any Serious AE		X	X
	Any Vaccine-Related AE		X	X
	Any Serious and Vaccine-Related AE		X	X
	Discontinuation due to AE		X	X
	Specific AEs, SOCs (incidence ≥ 4 of subjects in one of the treatment groups)		X	X
Tier 3	Specific AEs, SOCs (incidence < 4 of subjects in all of the treatment groups)			X

[†]Adverse Experience references refer to both Clinical and Laboratory AEs.
 Note: SOC=System Organ Class; X = results will be provided.

8.6.3 Summaries of Demographic and Baseline Characteristics

The comparability of the treatment groups for each relevant characteristic will be assessed by the use of tables and/or graphs. No statistical hypothesis tests will be performed on these characteristics. The number and percentage of subjects screened, randomized, the primary reasons for screening failure, and the primary reason for discontinuation will be displayed. Demographic variables, baseline characteristics, and prior and concomitant therapies will be summarized by treatment either by descriptive statistics or categorical tables.

8.7 Interim Analyses

Two interim analyses will be conducted during this study: (1) A first interim analysis will be performed when ~100% of the vaccinated subjects in the adult cohort and small infant cohort have completed postvaccination safety follow-up (single dose for adult cohort and postdose 3 for the small infant cohort) and ~100% of the immunogenicity results of IgG responses for adults (postvaccination) and small infant cohort (postdose 3) are available; (2) A second interim analysis will be performed in this study when ~100% of PD3 immunogenicity results for all infants in Stage 2 (small and large cohorts) are available. An internal statistician and statistical programmer assigned to the protocol will be unblinded throughout the duration of the study to facilitate the performing of the interim analysis as well as creation of the eDMC safety reports for ongoing safety review. Results of the interim analysis will be provided to the eDMC, and group summaries will be reviewed by the Sponsor's study team. The Sponsor's study team (except for the MRL statistician and programmer) will be blinded to the V114 formulation at the subject level. The Sponsor's study team will use the results to

make scientific decisions regarding future studies. It may also inform certain scientific consultations. No multiplicity adjustments will be made in either interim analysis as the conduct of the study will not be altered.

The endpoints, timing, and purpose of the interim analyses are summarized in [Table 6](#).

Table 6 Summary of Interim Analysis Strategy

Interim Analysis	Key Endpoints of Interim Analysis	Timing of Interim Analysis	Purpose of Interim Analysis
Adult and small infant cohort	
Adult GMC ratios for each of the 15 serotypes contained in V114.Adult GMCs at baseline and 1 month postvaccination, GMFR and % of subjects who achieved at least 4-fold rise at 1 month postvaccination for each of the 15 serotypes contained in V114.Adult percentage of subjects with any AE, a vaccine related AE, a serious AE, an AE which is both vaccine-related and serious, and who discontinued due to an AE.Small infant cohort PD3 GMCs and GMC ratios, for the 15 serotypes contained in V114.Small infant cohort PD3 proportion of subjects of subjects achieving concentrations $\geq 0.35 \mu\text{g/mL}$ and differences, for each of the 15 serotypes in V114.Percentage of infants in the small cohort with any AE, a vaccine related AE, a serious AE, an AE which is both vaccine-related and serious, and who discontinued due to an AE after each vaccination.	~100% of the adult cohort and small cohort of infants have completed safety follow-up (postvaccination for adult cohort and postdose 3 for small infant cohort) and ~100% of the immunogenicity results (IgG responses) for adult (postvaccination) and small infant (postdose 3) cohorts are available.	Inform scientific decisions for future studies

Interim Analysis	Key Endpoints of Interim Analysis	Timing of Interim Analysis	Purpose of Interim Analysis
All Infant Cohorts	
• Infant PD3 GMCs and ratios, for the 15 serotypes contained in V114.• Infant PD3 proportion of subjects achieving IgG concentrations $\geq 0.35 \mu\text{g/mL}$ and differences, for each of the 15 serotypes in V114.• Infant PD3 percentage of subjects with any AE, a vaccine related AE, a serious AE, an AE which is both vaccine-related and serious, and who discontinued due to an AE.	~100% of PD3 immunogenicity results (IgG responses) for all infants (small and large cohorts) are available.	Inform scientific decisions for future studies

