Duration of Participation	
Stage 1 - Adult Cohort: Each subject will participate in the trial for approximately 30 days from the time the subject signs the Informed Consent Form (ICF) through the final contact. Each subject will receive a single dose of the study vaccine on Day 1. After vaccination, each subject will be followed for 14 days for adverse experiences (AEs). Serious AEs (SAEs) will be collected from the time the consent is signed through completion of the subject's participation in the study (i.e., 30 days postvaccination). Blood samples will be collected prior to vaccination and 30 days postvaccination.

	Stage 2 - Infant Cohort: Each subject will participate in the trial for approximately 11 to 14 months from the time the parent/legal guardian signs the ICF through the final contact. Each subject will receive 4 doses of the study vaccine given at 2, 4, 6, and 12 to 15 months of age. After each vaccination, the study subject will be followed for 14 days for AEs. SAEs will be collected from the time the consent form is signed through 30 days postdose 4 (PD4) and/or completion of the subject's participation in the study. Blood samples will be collected 30 days following the 3 rd dose, immediately prior to the 4 th dose, and 30 days following the 4 th dose.
Randomization Ratio	Stage 1 (adult cohort): 1:1:1:1 Stage 2 (infant cohort): 1:1:1:1:1

A list of abbreviations used in this document can be found in Section 12.5.

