2.0 TRIAL DESIGN

2.1 Trial Design

This is a multicenter, randomized, double-blind (with in-house blinding procedures) study to evaluate the safety, tolerability, and immunogenicity of 4 different formulations of V114 in healthy adults and infants to be conducted in conformance with Good Clinical Practices (GCPs) at approximately 24 sites in the United States (US). Prevnar 13TM (pneumococcal 13-valent conjugate vaccine [diphtheria CRM₁₉₇ protein], Wyeth Pharmaceuticals, Inc., Philadelphia, Pa) will serve as an active control in the infant stage of the study. This study will enroll approximately 80 healthy adults 18 to 49 years of age (Stage 1) and 250 healthy infants 6 to 12 weeks (\geq 42 to \leq 90 days) of age (Stage 2). Prior to enrollment of infants, the safety and tolerability of a single-dose of the study vaccine must be demonstrated in healthy adults. Similarly, the safety and tolerability of the first dose of study vaccine must be demonstrated in a small cohort of infants prior to enrollment of the full infant cohort.

Stage 1 - Adult Cohort:

A total of 80 adult subjects will be randomly assigned to 1 of 4 formulations of V114:

- (1) Merck investigational V114 medium (N=20)
- (2) Merck investigational V114 high (N=20)
- (3) Merck investigational V114 medium with an alternative carrier protein (N=20)
- (4) Merck investigational V114 high with an alternative carrier protein (N=20)

The adult stage of this study is designed to evaluate the safety and tolerability of a single dose of 4 different formulations of V114 when administered intramuscularly to 80 healthy adults (20 per vaccination group).

Adverse events will be collected for 14 days following vaccination. After completion of a review of safety data from the adult cohort by an external Data Monitoring Committee (eDMC), Stage 2 of the study will begin.

Stage 2 - Infant Cohort:

Stage 2 will consist of 2 parts (Part I and Part II) during which a 0.5mL intramuscular dose of the study vaccine will be administered to healthy infants at 2, 4, 6, and 12 to 15 months of age. Each formulation of V114 will be first evaluated in a small number of infants (n=50) during Part I before initiating Part II which will enroll the remaining 200 infants. Prevnar 13TM will serve as control in both Part I and Part II.

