5.3 Randomization or Vaccine Allocation

Randomization will occur centrally using an interactive voice response system / integrated web response system (IVRS/IWRS). There are 4 V114 adult vaccination arms. Subjects will be assigned randomly in a 1:1:1:1 ratio to each of the 4 V114 vaccination groups in Stage 1, for the adult cohort. The infant cohort (Stage 2) will have 5 vaccination arms during which subjects will be randomly assigned in a 1:1:1:1:1 ratio to each of the 4 V114 vaccination groups or control (Prevnr 13™), respectively. Each formulation of V114 will be first evaluated in a small number of infants (10/arm) during Part I before initiating Part II, which will enroll the remainder of the infant cohort.

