Serum samples (approximately 40 mL) collected on Day 1 prior to vaccination and on Day 30 postvaccination will be used to measure vaccine-induced immune responses (IgG) to the 15 serotypes contained in V114. These serum samples will be assayed using the Meso-Scale Discovery MSD Pn ECL assay, which was developed by Merck & Co., Inc. for the measurement of pneumococcal capsular polysaccharide IgG antibodies. After completion of protocol-specified immunogenicity assays, leftover sera may be used for the development of future pneumococcal assays. Any remaining sample will then be retained for future biomedical research providing the future biomedical research (FBR) consent has been signed.

Stage 2: Infant Cohort

Subjects will have blood drawn (approximately 4-5 mL) at 3 time points: (1) Day 30 following the third study vaccination (PD3), (2) immediately prior to administration of the fourth study vaccination, and (3) Day 30 following the fourth study vaccination (PD4). Sera

will be used to measure vaccine-induced immune responses (IgG and opsonophagocytic killing activity [OPA]) to all 15 vaccine serotypes included in V114. These serum samples will be assayed using the Meso-Scale Discovery MSD Pn ECL assay, which was developed by Merck & Co., Inc. for the measurement of pneumococcal capsular polysaccharide IgG antibodies. Serum samples will also be assayed using a 4-Fold Multiplex Opsonophagocytic Assay which Merck has developed and implemented in collaboration with [REDACTED]

[REDACTED] from the University of Alabama. If a serum sample does not have enough volume for both the IgG and OPA testing, the IgG testing will take priority. OPA will be evaluated in approximately 50% of subjects with sufficient PD3 sera available to perform both the PnECL and the OPA testing on all 15 serotypes in V114. PD4 OPAs will be conducted for all of the subjects who had PD3 OPAs performed and for which there is sufficient serum. Leftover sera may also be used for the development of future pneumococcal assays. Any remaining sera will be retained for future biomedical research providing the future biomedical research (FBR) consent has been signed.

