8.6 Statistical Methods

8.6.1 Statistical Methods for Efficacy Analyses

This section describes the statistical methods that address the primary and secondary objectives. Methods related to exploratory objectives will be described in the supplemental SAP.

Analysis of the immunogenicity data from the infant stage of the study will be based on the combined data from Stage 2 Part I and Stage 2 Part II.

To address the primary infant immunogenicity objective #2, GMCs at 1 month PD3 along with two-sided 95% CIs will be computed for the 15 serotypes in V114 for V114 medium, V114 high, and 13 serotypes in Prevnar 13TM. Point estimates of GMCs are the exponentiated estimates of the mean log_e concentrations. The confidence intervals for GMCs are the exponentiated confidence intervals for the mean log_e concentrations, based on 1-sample t-distributions. Additionally, GMC ratios (V114/Prevnar 13TM) along with two-sided 95% CIs will be computed for each of V114 medium and V114 high relative to Prevnar 13TM for the 13 common serotypes. The CI for the ratio will be calculated using a 2-sample t-test approach based on the natural logarithm of the ratio.

To address the secondary infant immunogenicity objective #1, the proportion of subjects achieving the serotype-specific threshold value of $\geq 0.35\mu\text{g}/\text{mL}$ for the 15 serotypes at 1 month PD3 along with the 95% CI will be calculated for V114 medium, V114 high, and the 13 serotypes in Prevnar 13TM. The one-sample two-sided CIs will be computed using the exact CI method for a single binomial proportion given in Collett [7]. Additionally, the

difference (V114 minus Prevnar 13TM) in the proportion of subjects achieving an IgG concentration $\geq 0.35\mu\text{g/mL}$ along with two-sided 95% CIs will be computed for each of V114 medium and V114 high relative to Prevnar 13TM for the 13 serotypes in common. The CI for the difference will be computed using the method of Miettinen and Nurminen [8].

The additional secondary infant immunogenicity objective (#2) as well as the secondary adult immunogenicity objective #1 will utilize similar statistical methods as those outlined above.

Reverse cumulative distribution functions for both IgG and OPA levels at PD3 and PD4 will be graphically displayed by serotype in the CSR.

Table 4 summarizes the key immunogenicity analyses.

Table 4 Analysis Strategy for Key Immunogenicity Variables

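### Adult interim GMC ratios have no named arms or stated method, and no adjustment for the Day 1 IgG collected from every adult is planned

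*Combined protocol and SAP*

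**What the plan says.** **The endpoint.** In section 8.7, Table 6 opens the list for the first interim analysis with "Adult GMC ratios for each of the 15 serotypes contained in V114". It gives no numerator, denominator or method. The next entry is "Adult GMCs at baseline and 1 month postvaccination, GMFR and % of subjects who achieved at least 4-fold rise at 1 month postvaccination". The stated purpose is to inform decisions about future studies.

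**The adult design.** Section 2.1 plans "80 healthy adults (20 per vaccination group"). Section 5.3 says "Subjects will be assigned randomly in a 1:1:1:1 ratio to each of the 4 V114 vaccination groups in Stage 1". No adult receives Prevnar 13, and section 5.4 plans no stratification.

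**Day 1 IgG.** Section 1.0 says for adults: "Blood samples will be collected prior to vaccination and 30 days postvaccination". Section 7.1.3.1 says the adult sera "collected on Day 1 prior to vaccination and on Day 30 postvaccination will be used to measure vaccine-induced immune responses" to the 15 V114 serotypes.

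**The methods.** Section 8.6.1 sets out the infant GMC ratio of V114 to Prevnar 13 and states: "The CI for the ratio will be calculated using a 2-sample t-test approach based on the natural logarithm of the ratio". For adults it says only that "the secondary adult immunogenicity objective #1 will utilize similar statistical methods as those outlined above". That objective (section 3.2) covers GMCs and fold-rises for V114 medium and V114 high, and Table 4 gives it within-group estimates only. The adult alternative-carrier arms are exploratory (section 3.3), and section 8.6.1 leaves exploratory methods to the supplemental SAP. Section 8.10 plans no analysis of baseline factors.

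**The concern.** A key interim endpoint cannot be computed from the plan as written. Four arms allow 4 × 3 / 2 = 6 pairwise ratios per serotype, and the infant default of V114 over Prevnar 13 is not available. The internal statistician and programmer are unblinded throughout (sections 5.2.3, 8.2 and 8.7), so an undefined contrast and model could be settled by people who can already see results by arm.

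The second part is precision. If the one ratio method in the plan is borrowed, the adult ratio will not use Day 1 IgG, although that value will be on file for every adult. With 20 per arm, a chance difference in baseline IgG between two arms passes into the unadjusted ratio to the extent that baseline predicts response. These ratios are meant to inform later studies, so their width and their exposure to chance imbalance matter somewhat, even though nothing in this trial's conduct depends on them.

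**Working it through.** **1. The plan's own figures.** The plan gives no precision or power figure for adult ratios, so the check starts from the infant figures in section 8.9.

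- Table 7, with SD 1.0, a 2-fold difference, 45 per arm and one-sided alpha 0.05: the non-centrality is ln 2 / (1.0 × √(2/45)) = 0.693 / 0.211 = 3.29 on 88 df. The non-central t gives 94.71%, against 94.7% stated.
- Table 8, with SD 1.0 and GMC 1.0: exp(±t(0.975, 44) × 1.0/√45) = exp(±0.300) = 0.74 to 1.35, as stated.

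The plan's log-normal working is therefore understood correctly.

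**2. Inputs for adults.**

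- n = 20 per arm (section 2.1).
- ln SD = 1.0. This is an assumption: no adult SD is given, and the 0.8 to 1.4 range in section 8.9 comes from V114-003, an infant trial.
- Correlation ρ between ln Day 1 and ln Day 30 IgG. This is also an assumption: none is given, so it is varied from 0 to 0.7.

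**3. Unadjusted ratio.** The log half-width is t(0.975, 38) × SD × √(2/20) = 2.024 × 1.0 × 0.316 = 0.640. The factor is exp(0.640) = 1.90, so a true ratio of 1 gives 0.53 to 1.90.

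**4. ANCOVA on ln Day 1 IgG, two arms.** The log half-width is t(0.975, 37) × SD × √(1 − ρ²) × √((2/20)(1 + 1/36)). The term 1 + 1/36 is the expected cost of estimating the slope. At SD 1.0 this is 2.026 × 0.3206 × √(1 − ρ²) = 0.650 × √(1 − ρ²).

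| ρ | log half-width | factor | CI at true ratio 1 | change in log width |
|---|---|---|---|---|
| 0 | 0.650 | 1.91 | 0.52 to 1.91 | +1.5% |
| 0.3 | 0.620 | 1.86 | 0.54 to 1.86 | -3% |
| 0.5 | 0.563 | 1.76 | 0.57 to 1.76 | -12% |
| 0.7 | 0.464 | 1.59 | 0.63 to 1.59 | -27% |

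Break-even is where √(1 − ρ²) = 0.640/0.650, which is ρ of about 0.17. A simulation of 5,000 trials at each ρ gave log-width ratios of 1.014, 0.968, 0.878 and 0.725, with coverage between 94.4% and 95.2%.

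**5. Sensitivity to the SD.** The percentage changes do not depend on the SD, but the factors do. At SD 0.8 the factor goes from 1.67 unadjusted to 1.57 (ρ = 0.5) or 1.45 (ρ = 0.7). At SD 1.4 it goes from 2.45 to 2.20 or 1.91.

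**6. Whether the planned fold-rises already do this.** A ratio of fold-rises has log half-width t(0.975, 38) × SD × √(2(1 − ρ)) × √(2/20), if the pre and post SDs are equal (an assumption). At SD 1.0 the factor is 2.13, 1.90 or 1.64 at ρ = 0.3, 0.5 or 0.7. It is 18% wider on the log scale than the unadjusted ratio at ρ = 0.3, equal to it at 0.5, and wider than ANCOVA at all three values.

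**7. Chance imbalance.** The standard error of a baseline difference is 0.316 SD. At SD 1.0 (pre and post) and ρ = 0.5, a one-standard-error imbalance moves the unadjusted log ratio by 0.5 × 0.316 = 0.158, or about 17%.

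**The case against.** The strongest reply is that the plan has not chosen the method being criticised. A reader might infer from section 8.6.1 that the two-sample t is the stated method for adult ratios. The documents do not support that. The carry-over sentence covers an adult objective with no between-arm ratio, and Table 4 gives adults within-group estimates only. This stands. It makes the gap more basic, because the endpoint then has no method at all.

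A reader might also infer that the plan ignores baseline IgG. It does not: baseline GMCs, GMFR and the 4-fold-rise percentage all use it, so an imbalance would be visible. Only the ratio is without a planned adjustment, and step 6 shows that fold-rises are not an equivalent replacement.

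The gain is also unproven. It depends on a correlation that the documents do not give. It is slight at 0.3 and turns into a small loss below about 0.17. That stands, so the plan cannot be called needlessly imprecise as a matter of fact.

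The method may also have been left to the supplemental SAP, which is not available here. That is plausible for contrasts involving the alternative-carrier arms. The high/medium ratio within CRM197 involves only the two arms covered by the secondary objective, and it too lacks a method here.

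Finally, the stakes are low. The adult stage is sized for safety (section 8.9), the study is estimation only (section 8.3), and section 8.7 says the interims will not alter conduct. This is correct and limits the point to a minor one.

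**Conclusion.** The point holds as a minor one, in two parts. First, Table 6 lists an adult GMC ratio with neither arms nor method, and nothing elsewhere in the protocol or SAP supplies them. This rests on the text alone. Second, no adjustment of that ratio for Day 1 IgG is planned, although the measurement is already scheduled for every adult. The benefit of adding it is conditional: at 20 per arm the log width falls by 12% at a correlation of 0.5 and 27% at 0.7, against 3% at 0.3 and a 1.5% increase at 0. The factor of 1.90 rests on the assumed adult SD of 1.0, and all the percentages rest on the assumed correlation.

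A reader might take this to mean that the planned adult ratio would be biased. It would not be: under randomisation the unadjusted ratio is a valid estimate, and chance imbalance is already part of its standard error. The case for adjustment is efficiency. It does not extend to the infant ratios at one month postdose 3, because infants have no sample before dose 1 (section 4.2.3.1).

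**What to change.** In Table 6 and section 8.6.1, or in the supplemental SAP before any adult IgG result is seen by arm:

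- Name the adult contrasts: high over medium within each carrier, and alternative carrier over CRM197 within each dose level. That is four ratios per serotype.
- Estimate each ratio, by serotype, from an ANCOVA of ln Day 30 IgG on arm and ln Day 1 IgG, with a two-sided 95% CI.
- Report the unadjusted two-sample t ratio as supportive.
- State whether the model is fitted to each pair of arms or once to all four. The figures above are for pairs. A four-arm model with common slope and variance gives slightly lower factors of 1.83, 1.73 and 1.57 at correlations 0.3, 0.5 and 0.7.
- Keep the within-arm GMCs, fold-rises and 4-fold-rise percentages as planned.

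The cost is a few lines of text, one degree of freedom, and a log width about 1.5% greater if the correlation is zero. An adult without a valid Day 1 result would drop out of the adjusted ratio but stay in the unadjusted one. No new samples or assays are needed.
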